One pharmacokinetic clinical study was conducted with P3P in 19 smokers in Switzerland (ClinTrials.gov: NCT03369340). In this study, following a single use of four P3P variants, nicotine  $C_{max}$  was 1.1 ng/mL for the 1 mg variant and between 2.1 and 3.1 ng/mL for the 2 mg variants and was reached after 15-22.5 minutes ( $T_{max}$ ).  $C_{max}$  values for P3P were lower compared to literature-reported  $C_{max}$  for cigarettes which ranges between 10-30 ng/mL (23-25) or Nicorette® Inhalator, a nicotine replacement therapy, for which  $C_{max}$  values of 6-8 ng/mL have been described (25, 26).  $T_{max}$  was at a later timepoint for P3P compared to cigarettes for which maximal plasma concentration is reached after 5-8 minutes, but earlier compared to Nicorette® Inhalator for which  $T_{max}$  is at 30 minutes. Thus, the observed concentration-time profile for P3P is indicative of a partial pulmonary and partial oromucosal absorption compared to the pulmonary absorption for cigarettes and the oromucosal absorption of Nicorette® inhalator. The adaptation of the product use behavior in these subjects, which were unfamiliar with P3P may have been incomplete. The product was generally well tolerated and no safety concern was revealed.

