#### **Confidentiality Statement**

Data and information contained in this document are considered to constitute trade secrets and confidential commercial information, and the legal protections provided to such trade secrets and confidential information are hereby claimed under the provisions of applicable law. No part of this document may be publicly disclosed without the written consent of Philip Morris Products S.A.

In a previous study conducted with P3P (ClinTrials.gov: NCT03369340), the pharmacokinetic profiles of nicotine following a single use of P3P were indicative of a partial pulmonary and partial oromucosal absorption with lower plasma nicotine levels compared to published data for single cigarette smoking (23, 24). It is well established that changing a current cigarette to a novel tobacco /nicotine-containing product requires an adaptation in product use behavior as has been described for low-yield cigarettes, e-cigarettes or a novel Tobacco Heating System (10-15). The changes in product use behaviour over time (e.g. potential changes in puffing/inhalation process) may result in changes in the nicotine PK profiles in particular in the absorption phase. For this reason, nicotine PK profiles and parameters following a single product use will be assessed at the beginning of the exposure period (Day 1) and at the end of the exposure period following adaptation to product use (Day 30). Sampling timepoints for determination of nicotine concentrations were selected to ensure reliable estimation of PK parameters.

Plasma nicotine presents a biphasic profile, with a typical rapid initial disposition half-life ( $t_{1/2\alpha}$ ) of 1.35 hours, followed by a slower terminal elimination half-life ( $t_{1/2\beta}$ ) of 17 hours (28). To ensure a full nicotine washout between each product use, a separation of 3 days would have been required ( $\sim 5 \times$  elimination  $t_{1/2\beta}$ ). Based on nicotine population PK modeling, it was estimated that subjects' nicotine has entered in the terminal elimination phase with concentrations decreasing according to the terminal elimination rate constant ( $\lambda_z$ ) after 8 to 10 hours post administration. As a consequence, a minimum of 10 hours have been established in this study design before the start of product use for PK assessment to ensure appropriate washout of nicotine. Background-concentration correction will be applied to adjust for any residual carry-over effects as detailed in section 12.5.1.

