#### 12.1.2 Definitions for Statistical Data Analysis

For plasma nicotine time-concentration and VAS-craving, baseline will be defined as the last measurement prior to product use for PK assessment (prior to T0)

For the changes from baseline in PK parameters, PD parameters, CYP2A6 and product acceptance, described in sections 3.1 and 3.2, Day 1 value will be considered as the baseline. For BoExp and safety parameters the last assessments prior to product test will be considered as baseline.

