### 12.5.3 Statistical Analysis

PK parameters will be summarized as described in section 12.1.3.

Nicotine PK profiles will be summarized and plotted over time for each visit.

An analysis of variance (ANOVA) will be conducted for Day 1 and Day 30 on background-corrected  $AUC_{(0-4h)}$  and background-corrected  $C_{max}$  endpoints in the natural logarithmic scale. The model will include sex as a covariate. The results of this analysis for each of  $cAUC_{(0-4h)}$  and  $cC_{max}$  will be presented as geometric least square means and 95% confidence intervals for each variant and least square mean ratio and 95% confidence intervals of P3P-2mg:P3P-1mg ratio.

For the ANOVA tests, the following hypothesis will be tested:

$H_0: \mu_1 = \mu_2$

$H_1: \mu_1 \neq \mu_2$

where  $\mu_1$  and  $\mu_2$  are the means (arithmetic or geometric) for each product variant, respectively.

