5.3 Study Hypotheses And Evaluation Criteria

5.3.1 Hypotheses

The study will be descriptive in nature. However, for the ANOVA tests, the following hypothesis will be tested:

$$H_0: \mu_1 = \mu_2$$

$$H_1: \mu_1 \neq \mu_2$$

where μ_1 and μ_2 are the means (arithmetic or geometric) for each product variant, respectively.

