6 INVESTIGATIONAL PLAN

6.1 Study Design

This is a randomized, double-blinded, 2-arm parallel groups, single-center study conducted in current adult smokers willing to switch from smoking cigarettes to using P3P for 1 month. Subjects were asked to use no more than 15 P3P products per day over 1 month and the study will include 2 occasions of confinement period (3 days at V2 and 2 days at V6). From the start of the exposure period onwards, subjects will be instructed to use P3P exclusively. Subjects will be randomized to use either P3P-2mg or P3P-1mg.

1) Screening and Admission (from the ICF Signature [V1] to Randomization at V2 [Day -1]):

A Screening Visit will be conducted within 3 weeks prior to Admission to the investigational site. A demonstration of P3P, without product use, will be done by the investigational site staff during the Screening Visit.

Subjects will return to the investigational site for Admission (Day -1). Subjects should have been fasting for at least 6 hours prior to Admission. After confirmation of eligibility, subjects will be enrolled. All subjects that are not enrolled will be considered as screen failures. At Admission, enrolled subjects will perform a product test using up to 6 P3P products (alternating between P3P-1mg and P3P-2mg). In order to continue in the study, each subject will need to test at least one product of each P3P variant during the product test. Subjects should be abstinent from the use of any tobacco/nicotine containing products for at least 4 hours prior to product test. After the product test, subjects not willing and/or not ready to use P3P will be discontinued from the study. Subjects willing and ready to use P3P during the study will be randomized either to P3P-1mg or P3P-2mg in a 1:1 ratio and will start their first overnight (confinement) period for pharmacokinetics assessments on Day 1. The subjects and the Investigator will be blinded to the randomization arm.

2) The Exposure Period (from V2 [Day 1] to Discharge at V6 [Day 30]):

On Day 1, after at least 10 hour abstinence from any tobacco/nicotine containing products, subjects will use a single P3P product, as randomized, for a duration of up to 15 minutes. The start of product use will be defined as T_0 .

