6.3 Product Allocation and Blinding

6.3.1 Methods of Assigning Subjects to Product Variant

At Day -1, after product test, subjects who confirmed their willingness to continue in the study will be randomized using an interactive web response system (IWRS). Subjects will be randomized to one of the two arms: P3P-1mg or P3P-2mg in a 1:1 ratio.

Each randomization group (P3P-1mg, P3P-2mg) will be stratified on sex distribution to ensure that at least 40% of each sex is randomized in each group.

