12.5 Planned Statistical Analyses

12.5.1 Primary Analyses of PK parameters

An analysis of covariance (ANCOVA) will be conducted at Day 30 on background-corrected $AUC_{(0-4h)}$ ($cAUC_{(0-4h)}$) and background-corrected C_{max} (cC_{max}) endpoints in the natural logarithmic scale. The model will include sex and variant as factors and value at Day 1 in the natural logarithmic scale as a covariate. The results of this analysis for each of $cAUC_{(0-4h)}$ and cC_{max} will be presented as geometric least square means and 95% confidence intervals for each variant and least square mean ratio and 95% confidence intervals of P3P-2mg:P3P-1mg ratio.

The same ANCOVA analysis will be performed for the $AUC_{(0-4h)}$ and C_{max} derived using uncorrected concentrations.

LS means for each product will be back-transformed by exponentiation and will be tabulated together with the ratio (P3P-2mg:P3P-1mg) and 95% CI.

In addition, least square mean ratio and 95% confidence intervals of Day 30 versus Day 1 will be provided by variant using an ANOVA model for the difference Day 30 – Day 1 in the natural logarithmic scale endpoints; the ANOVA model will have variant and sex as factors. LS means for each product will be back-transformed by exponentiation.

The geometric CV will also be presented as $CV(\%) = 100\sqrt{(e^{MSE} - 1)}$, where MSE is the mean square error of the fitted model residual.

Descriptive statistics for t_{max} will be provided by P3P variant, the p-value resulting from the non-parametric between-group comparison (Wilcoxon Rank Sum Test) will be reported. The Hodges-Lehman estimate for the between-group difference in median will be reported together with its 95% CI.

Descriptive statistics will be presented by sex (male or female) and by product exposure category.

For t_{max} , descriptive statistics by sex and product exposure will also be provided.

To better understand the impact of the higher than expected T_0 values, a sensitivity analysis of the Background-Corrected and Uncorrected $AUC_{(0-4h)}$ and C_{max} will be performed where data for subjects with their T_0 value $>5\%$ of their C_{max} value will be excluded from the analysis.

The data will be presented in the below outputs:

TFL number	Title
TABLES	
15.2.9.1	Descriptive Statistics of Background-Corrected and Uncorrected Pharmacokinetic Parameters of Nicotine (AUC _(0-4h) and C _{max}) at Day 1 and Day 30 – PK Population

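### The Day 30 2mg:1mg PK ratio is adjusted for a Day 1 value that is itself an outcome of the randomized variant, so it is not the Day 30 variant ratio

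*SAP*

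**What the plan says.** SAP 6.3.1 places allocation before any PK session: "At Day -1, after product test, subjects who confirmed their willingness to continue in the study will be randomized". On Day 1, under SAP 6.1, "subjects will use a single P3P product, as randomized, for a duration of up to 15 minutes". The Day 1 cAUC(0-4h) and cCmax come from that use.

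SAP 12.5.1 then models the Day 30 log values. "The model will include sex and variant as factors and value at Day 1 in the natural logarithmic scale as a covariate". It reports geometric LS means by variant and the 2mg:1mg ratio with a 95% CI, for background-corrected and uncorrected parameters.

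The hypothesis in SAP 5.3.1 is H0: μ1 = μ2, where μ1 and μ2 "are the means (arithmetic or geometric) for each product variant, respectively". It does not condition on Day 1.

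Protocol 12.5.3 planned something different: "An analysis of variance (ANOVA) will be conducted for Day 1 and Day 30", with sex as the only covariate. SAP 9 replaces this with the Day 30 ANCOVA and drops the Day 1 comparison. It gives no reason and leaves H0 unchanged. For changes in PK parameters, protocol 12.1.2 says the "Day 1 value will be considered as the baseline".

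**The concern.** Calling Day 1 the baseline does not make it a pre-treatment value. Adjusting a randomized comparison for a variable that treatment has already changed removes part of the treatment effect, and the remaining contrast no longer compares the variants as randomized.

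This ANCOVA is the only between-variant inference that SAP 12.5.1 specifies for AUC and Cmax, and its table (15.2.9.2) is among the topline results in SAP 13.2. As written, a real twofold Day 30 difference can be reported as much smaller, and equal Day 30 means can be reported as a difference. The per-variant LS means are affected too, because both are evaluated at one common Day 1 value.

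**Working it through.** There is no plan figure to reproduce. The 60 subjects (about 30 per arm) are stated to be empirical, with no effect size or SD.

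**Inputs from the documents**
- Nicotine content is 1 mg versus 2 mg (protocol 6.1.1).
- In the earlier study described in protocol 2.1.2, single-use Cmax "was 1.1 ng/mL for the 1 mg variant and between 2.1 and 3.1 ng/mL for the 2 mg variants". This gives Cmax ratios of 2.1/1.1 = 1.91 to 3.1/1.1 = 2.82. No AUC ratio is given.
- Protocol 4.2 says that changes in use behaviour "may result in changes in the nicotine PK profiles in particular in the absorption phase", so R30 cannot be presumed equal to R1.

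**Assumptions, not in the documents**
- b = 0.3, 0.5 or 0.7.
- CV = 40%, 60% or 80%.
- The pairs of R1 and R30 shown below.

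**Formula.** With the log Day 1 value as covariate, the variant effect is ln R30 − b·ln R1, so the reported ratio targets R30/R1^b. It equals R30 only if R1 = 1 or b = 0. For example, 2.0/2.0^0.5 = 1.41.

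| R1 | R30 | b = 0.3 | b = 0.5 | b = 0.7 |
|---|---|---|---|---|
| 1.91 | 1.91 | 1.57 | 1.38 | 1.21 |
| 2.00 | 2.00 | 1.62 | 1.41 | 1.23 |
| 2.82 | 2.82 | 2.07 | 1.68 | 1.36 |
| 2.00 | 3.00 | 2.44 | 2.12 | 1.85 |
| 2.00 | 1.20 | 0.97 | 0.85 | 0.74 |
| 2.00 | 1.00 | 0.81 | 0.71 | 0.62 |

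When the ratio is the same on both days, 30%, 50% or 70% of the log effect is removed. For R1 above 1 and b above 0 the target is always below R30. Whether that moves it toward 1 or past 1 depends on R30.

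**LS means.** With equal arms, each variant's log mean shifts by b·ln(R1)/2. For R1 = 2 and b = 0.5 this is 0.5 × 0.693/2 = 0.173, and exp(0.173) = 1.19. The 1 mg mean is therefore about 19% too high and the 2 mg mean about 16% too low (1/1.19 = 0.84).

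**Simulation.** Bivariate normal logs, 30 per arm, sex balanced, equal SDs on both days. Where a range is shown, separate runs differed.

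| Scenario | Model | b = 0.3 | b = 0.5 | b = 0.7 |
|---|---|---|---|---|
| R1 = R30 = 2, CV 60%: 95% CI covers 2.0 | ANCOVA | 76% | 36–39% | 3% |
| Same, CV 40% | ANCOVA | 64% | 18% | 0.2% |
| Same, CV 80% | ANCOVA | 82% | 53% | 11% |
| R1 = R30 = 2, CV 60%: CI excludes 1 | ANCOVA | 83% | 62% | 37% |
| R1 = 2, R30 = 1, CV 60%: CI excludes 1 | ANCOVA | 23–26% | 63–65% | 97% |

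At CV 60%, ANOVA with variant and sex only covers 2.0 in about 95% of trials and excludes 1 in over 99% when both ratios are 2. It excludes 1 in about 4% to 5% when R30 = 1.

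**Related models.** The Day 30 between-variant models for VAS-craving AUC (SAP 12.5.2.1) and Product Experience (SAP 12.5.2.3) also adjust for a Day 1 value taken after use of the assigned product. The documents show no size for a Day 1 difference there, so the size of that bias is unknown.

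**Section 9.** SAP 9 says the protocol's ANOVA contained product exposure category and lists that factor in the ANCOVA. Protocol 12.5.3 has sex only, and SAP 12.5.1 has sex, variant and the Day 1 value. The category is average use over Days 1 to 29 (SAP 12.1.7), so it too is measured after randomization.

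**The case against.** The strongest reply is about purpose. The study is described as descriptive, its aim is adaptation over a month, SAP 12.1.6 says no claim will rest on the CIs, and the primary objective names no contrast between variants. The within-variant Day 30/Day 1 ratios answer the adaptation question and are unaffected, as is the tmax test. H0 names no day, and comparing variants at equal Day 1 values is a definable estimand that SAP 9 openly declares. Table 15.2.9.1 should give geometric means with CIs per arm on both days, so a reader could form the unadjusted ratio.

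Part of this stands. The contrast is definable, but the SAP does not define it: it labels the result the 2mg:1mg ratio, keeps H0 in terms of variant means, and tests the variants on AUC and Cmax only at Day 30. Per-arm summaries do not supply a planned CI for the ratio. Table 15.2.11.1, a sensitivity analysis titled for both days, states no model and excludes subjects with high T0 values, so it does not fill the gap. The no-claim statement answers multiplicity, not a mislabelled primary estimate.

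The limits on size also stand. No document gives b or CV. R1 of 1.9 to 2.8 rests on one study of 19 smokers and concerns Cmax. Uncorrected values contain carry-over nicotine, which pulls R1 toward 1, so the figures do not transfer directly to the uncorrected models. The 97% figure needs R1 = 2, R30 = 1 and b = 0.7 together.

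Precision is not a strong defence. With R1 = 2 and CV 60%, the median ratio of upper to lower 95% limit is 1.77 for ANOVA, against 1.91, 1.81 and 1.63 for the ANCOVA at b = 0.3, 0.5 and 0.7.

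**Conclusion.** The concern holds, and the primary between-variant analysis is wrong as written. The structural fault does not depend on the assumed values: the covariate follows randomization and use of the assigned variant, so the ratio targets R30/R1^b. How far this departs from R30 depends on R1 and b. The protocol's own Cmax figures make R1 well above 1 plausible, and b near 0 would leave the covariate with no purpose. For a common ratio of 2.0 and b from 0.3 to 0.7, the reported ratio would be 1.62 down to 1.23. There is no bias if R1 = 1 or b = 0.

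**What to change.** - In SAP 12.5.1, make the protocol 12.5.3 model primary: ANOVA of ln cAUC(0-4h) and ln cCmax, and of the uncorrected values, with variant and sex and no Day 1 PK covariate. Report the 2mg:1mg ratio and 95% CI at Day 30 and at Day 1.
- Keep the Day 30 minus Day 1 ANOVA for adaptation, and also report its between-variant ratio of changes with a 95% CI.
- The ANCOVA may stay as supportive if its estimand is stated: the Day 30 ratio at an equal Day 1 value.
- Make the same change to the Day 30 between-variant models in SAP 12.5.2.1 and 12.5.2.3. For VAS craving this returns to protocol 12.6.2. For Product Experience the protocol left the analysis to the SAP.
- Correct SAP 9 so that it matches 12.5.1 and describes protocol 12.5.3 accurately, and leave product exposure category out of the between-variant model.

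The cost is SAP wording and simpler model code, with no new data. At CV 60% and R1 = 2, precision is lost only at the highest slope examined (b = 0.7). The ANOVA also keeps subjects with a Day 30 but no Day 1 profile. The PK population definition admits them, but the ANCOVA would drop them.

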## 2.2 Purpose of the Study

The purpose of the study is to evaluate the adaptation of product use in adult, current cigarette smoking subjects between baseline and after 1 month of use of one of two P3P variants.

The effect of P3P use behavior on nicotine pharmacokinetic (PK) profile, acceptability, as well as the safety and tolerability of P3P over a period of 1 month will be investigated. In addition, the overall use of tobacco and nicotine containing products will be monitored.

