9 CHANGES FROM THE PROTOCOL SPECIFIED STATISTICAL ANALYSIS

The following changes with respect to the analysis populations were made in the SAP compared to the Protocol:

- Changes regarding Population of Subjects to be Used for Different Endpoints

Endpoints	Protocol	SAP
Pharmacodynamics (VAS craving, Sensory questionnaire, ABOUT™ -Product Experience)	PK	Randomized
Product Acceptance	PK	Randomized
Puffing Inhalation Behavior	PK	Randomized

In addition, results for the 2 variants combined will not be reported except for data collected at baseline.

- Changes regarding Analysis Model for PK and AUC for VAS craving score

In the protocol, an ANOVA model with sex and product exposure category as factors was anticipated to be used to compare PK parameters and AUC for VAS craving score between variants at Day 30. The ANOVA model was replaced by an ANCOVA model with sex and product exposure category as factors and Day 1 value as covariate.

No Day 1 comparisons will be performed. Within-group comparisons Day 30 versus Day 1 will also be performed in an ANOVA model with sex and product exposure category as factors.

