12.5.2 Secondary Analyses

12.5.2.1 VAS Craving score

At Day 30, an analysis of covariance (ANCOVA) will be performed on the AUC for the VAS craving score over the duration 0-4h post T₀ denoted AUC_{VAS Craving (0-4h)}. The model will have P3P variant and sex as factors and Day 1 value as covariate. Comparisons between variants will be performed and LSmeans differences between variant reported with their 95% CI. LSMeans and 95% CI for the AUC_{VAS Craving (0-4h)} by variant will also be reported.

Changes from baseline at Day 30 in AUC_{VAS Craving (0-4h)} will also be analyzed in an ANOVA model with variant and sex as factors. Within-group changes from baseline will be estimated using LSMeans and 95% CI.

Descriptive Statistics of AUC_{VAS Craving (0-4h)} at Day 1 and Day 30 and Change from Day 1 at Day 30 Overall; By Sex and By Exposure Category will be provided.

VAS craving score at Day 1 and Day 30 and changes from Day 1 value will be summarized in a descriptive manner by timepoint and P3P variant.

TFL number	Title
TABLES	
15.2.13.1	Descriptive Statistics of AUC _{VAS Craving (0-4h)} at Day 1 and Day 30 and Change from Day 1 at Day 30 – Randomized Population
15.2.13.2	Analysis of AUC _{VAS Craving (0-4h)} at Day 1 and Day 30 and Change from Day 1 at Day 30 – Randomized Population
15.2.13.3	Descriptive Statistics of AUC _{VAS Craving (0-4h)} at Day 1 and Day 30 and Change from Day 1 at Day 30 – By Sex - Randomized Population
15.2.13.4	Descriptive Statistics of AUC _{VAS Craving (0-4h)} at Day 1 and Day 30 and Change from Day 1 at Day 30 – By Product Exposure Category - Randomized Population
15.2.13.5	Descriptive Statistics of VAS craving score at Day 1 and Day 30 and Change from Day 1 at Day 30 by Timepoint – Randomized Population
15.2.13.6	Descriptive Statistics of VAS craving score at Day 1 and Day 30 and Change from Day 1 at Day 30 by Timepoint by Sex – Randomized Population
15.2.13.7	Descriptive Statistics of VAS craving score at Day 1 and Day 30 and Change from Day 1 at Day 30 by Timepoint by Product Exposure Category – Randomized Population
FIGURES	
15.3.3.1	VAS Craving Score Profiles By Timepoint at Day 1 and Day 30 – Randomized Population
15.3.3.2	Individual VAS profiles – Randomized Population

TFL number	Title
LISTINGS	
15.1.13.1	Listing of AUCVAS Craving (0-4h)
15.1.13.2	Listing of VAS craving scores

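### The Day 30 versus Day 1 models for PK and craving report only within-variant change, and the Day 30 ANCOVA ratio does not supply the between-variant difference in adaptation

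*SAP*

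**What the plan says.** The design is a two-arm randomised comparison: "Subjects will be randomized to one of the two arms: P3P-1mg or P3P-2mg in a 1:1 ratio" (SAP 6.3.1). Protocol 2.2 gives the aim: "The purpose of the study is to evaluate the adaptation of product use in adult, current cigarette smoking subjects", from baseline to one month on one of the two variants.

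SAP 12.5.1 plans two model-based analyses of background-corrected AUC(0-4h) and Cmax on the log scale, and Table 15.2.9.2 carries both for the corrected and uncorrected parameters.

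- **Day 30 ANCOVA.** "The model will include sex and variant as factors and value at Day 1 in the natural logarithmic scale as a covariate". Its output is the P3P-2mg:P3P-1mg ratio with 95% CI.
- **Change model.** The response is log Day 30 minus log Day 1, and "the ANOVA model will have variant and sex as factors". Its stated output is that "least square mean ratio and 95% confidence intervals of Day 30 versus Day 1 will be provided by variant using an ANOVA model". No contrast between variants is listed.

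SAP 12.5.2.1 repeats the pattern for craving AUC. A Day 30 ANCOVA gives the between-variant difference. The change model has variant and sex as factors, and for it the stated output is: "Within-group changes from baseline will be estimated using LSMeans and 95% CI".

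SAP 9 describes the change analysis differently. It says "Within-group comparisons Day 30 versus Day 1 will also be performed" and then names sex and product exposure category as the factors, without naming variant. SAP 12.5.2.3 uses the same two factors for the within-group model of the Product Experience questionnaire.

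**The concern.** The plan yields one Day 30/Day 1 estimate per variant and one between-variant estimate at Day 30 adjusted for Day 1. A reader who wants to know whether the two variants differ in adaptation has nothing that estimates it directly. Two substitutes are at hand, and neither is sound.

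- **Comparing the two within-variant intervals by eye.** This is not an estimate of their difference and carries no interval of its own.
- **Reading the Day 30 ANCOVA ratio as a difference in adaptation.** The covariate is the Day 1 PK value. SAP 6.1 has that value measured after randomisation, on the allocated product. The variants differ in nicotine content, so they should already differ on Day 1. Holding Day 1 equal therefore compares low Day 1 values on P3P-2mg with high ones on P3P-1mg, and the ratio can lie well above 1 even when both variants adapt identically.

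What is at stake is how a secondary reading of the primary PK data is interpreted. The primary objective itself is not at risk.

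**Working it through.** The plan has no power or precision figure to reproduce: SAP 8 calls the sample size empirical and gives no effect size, SD or power.

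**Inputs**

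- About 30 per arm, 60 in total (SAP 8).
- Earlier single-use study: Cmax 1.1 ng/mL for the 1 mg variant and 2.1 to 3.1 ng/mL for the 2 mg variants (Protocol 2.1.2). As a guide to the Day 1 ratio: 2.1/1.1 = 1.91 and 3.1/1.1 = 2.82.
- Day 1 slope *b* within arm: not in the documents; 0.5 and 0.75 assumed.
- CV of the individual Day 30/Day 1 ratio: not in the documents; 30% to 100% assumed.

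**Step 1: what the ANCOVA estimates.** Let D be the log Day 1 ratio between variants and Δ the between-variant difference in mean log change. The between-variant difference in mean log Day 30 is D + Δ. The ANCOVA effect is that difference less *b* times the Day 1 difference:

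ANCOVA effect = D + Δ − bD = Δ + (1 − b)D.

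With equal adaptation (Δ = 0), the expected ratio is exp[(1 − b)D], which is the Day 1 ratio raised to the power (1 − b).

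**Step 2: put the numbers in, with Δ = 0.**

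| Day 1 ratio | b = 0.5 | b = 0.75 | b = 1 |
|---|---|---|---|
| 1.91 | 1.38 | 1.18 | 1.00 |
| 2.82 | 1.68 | 1.30 | 1.00 |

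Large simulations gave ANCOVA ratios of 1.38, 1.18, 1.68 and 1.29 for the four cells with b below 1. In each, the ratio of Day 30/Day 1 ratios was 1.00 to two decimals.

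**Step 3: one trial-sized illustration.** Simulated data had 30 per arm, Day 1 medians of 1.1 and 2.6 ng/mL, a Day 1 log SD of 0.6, slope 0.5, residual SD 0.5 and the same true change in both arms (0.3 on the log scale).

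- ANCOVA on Day 30: variant effect 0.526 (95% CI 0.237 to 0.815).
- ANCOVA on the change, with Day 1 as covariate: the same estimate and interval.
- Change model with variant and sex only: variant contrast 0.029 (95% CI −0.238 to 0.296).

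The first two agree because subtracting Day 1 from the response only shifts the covariate's coefficient by 1. The third is the quantity that the plan does not report.

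**Step 4: precision of the missing contrast.** With sd = √ln(1 + CV²), SE = sd × √(2/n) and 2n − 3 degrees of freedom, the 95% CI is the estimate multiplied or divided by exp(t × SE). For n = 30 and CV 30%: sd = 0.294, SE = 0.294 × 0.258 = 0.076, t = 2.00, giving a factor of 1.16. The ratio detectable with 80% power at two-sided 5% is exp[(1.96 + 0.84) × SE].

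| CV | CI factor, 30 per arm | Detectable ratio, 30 per arm |
|---|---|---|
| 30% | 1.16 | 1.24 |
| 50% | 1.28 | 1.41 |
| 70% | 1.39 | 1.58 |
| 100% | 1.54 | 1.83 |

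With 24 evaluable per arm (assumed), the CI factors run from 1.19 to 1.62 and the detectable ratios from 1.27 to 1.96.

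**The case against.** The strongest reply is that the plan already does what the study asks. The purpose is change over one month within users of one of two variants. The primary objective is PK on Day 1 and Day 30, and no objective names a difference in adaptation between variants. The per-variant ratios answer that purpose directly. This stands, and it limits the point to an improvement.

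A reader might infer several stronger things that the documents do not support.

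- **That the arms are never compared on change.** They are: Step 3 shows the Day 30 ANCOVA to be a comparison of change conditional on Day 1. What is missing is the unconditional difference in change.
- **That the SAP leaves its own hypothesis untested.** SAP 5.3.1 says "However, for the ANOVA tests, the following hypothesis will be tested", with equality of the variant means as the null. Protocol 12.5.3 attached that hypothesis to the between-variant ANOVA. SAP 9 replaced the ANOVA with the ANCOVA, which reports the between-variant contrast. The word ANOVA in 5.3.1 reads as left over.
- **That the contrast would cancel residual nicotine background.** Background enters additively (SAP 7.1), so it need not cancel in a ratio. For example, take an assumed 0.2 ng/mL left on Day 30 only, with Cmax 1.1 and 2.2 and no true change. The result is (2.4/2.2)/(1.3/1.1) = 0.92, not 1.
- **That the plan will misjudge the variants by setting two significance tests side by side.** SAP 5.3.1 calls the study descriptive, Protocol 12.1.5 marks the significance level as not applicable, and SAP 12.1.6 disclaims claims from individual intervals. No such decision rule is written.

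It is also fair to say that the contrast comes free from a fitted model only if 12.5.1 and 12.5.2.1 prevail over SAP 9. SAP 12.1.7 forms the exposure categories within variant, six in all, so SAP 9 may imply variant, but it does not say so. These sections must be reconciled first.

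**Conclusion.** The point holds in a limited form. For AUC(0-4h), Cmax and craving AUC, the change models specified in SAP 12.5.1 and 12.5.2.1 contain variant but report no between-variant contrast. The only between-variant estimate for these endpoints conditions on a post-randomisation Day 1 value that is expected to depend on the variant, so it does not estimate the difference in adaptation.

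For Cmax, the gap between the ANCOVA ratio and a true ratio of ratios of 1 is a factor of about 1.38 to 1.68 at slope 0.5 and 1.18 to 1.30 at slope 0.75. It vanishes at slope 1. The slopes are assumptions, and the Day 1 ratio is carried over from the earlier study. The documents give no such figures for AUC or craving AUC, so for those only the structure of the argument applies. The ANCOVA remains a legitimate analysis of Day 30 level given Day 1; the fault would lie in reading it as adaptation.

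**What to change.** 1. Reconcile the factors in SAP 9 (sex and product exposure category) with those in 12.5.1 and 12.5.2.1 (variant and sex), so that the change models are stated once and contain variant.
2. In SAP 12.5.1, from the change model, also report the P3P-2mg:P3P-1mg ratio of Day 30/Day 1 ratios with its 95% CI, for corrected and uncorrected AUC(0-4h) and Cmax. Add it to Table 15.2.9.2.
3. In SAP 12.5.2.1, from the change model, report the between-variant LS mean difference in craving AUC change with its 95% CI. Add it to Table 15.2.13.2.
4. State that any remark on variants differing in adaptation rests on these contrasts, not on the ANCOVA ratio and not on setting the two within-variant intervals side by side.

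The cost is SAP wording and one contrast per model. No new data or subjects are needed. The downside is one further interval per parameter, probably wide, which should be presented as descriptive like the rest.
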